9.4 Serious Adverse Event Reporting

Investigators are responsible for monitoring the safety of patients who have entered this study and for alerting the UMGCCC DSM/QAC to any event that seems unusual, even if this event may be considered an unanticipated benefit to the patient. Any adverse event that meets the definition of serious which occurs at any time during the clinical study or within 30 days of receiving the last dose of study medication, whether or not related to the study drug will be reported as follows:

All SAE’s, whether or not related to the study drug, will be reported via OnCore to the DSM/QAC according to the UMGCC DSM/QAC SOP.

Treatment-related toxicities and other adverse events will be monitored through standard medical practice, in addition to scheduled follow-ups as outlined in the treatment plan. Adverse events should be described according to the National Cancer Institute (NCI) Common Terminology Criteria for Adverse Events, v. 4.03 (Table 7). (see http://ctep.cancer.gov/protocolDevelopment/electronic_applications/ctc.htm).

Any serious adverse event, or follow up to a serious adverse event (including death due to any cause other than progression of the cancer under study) that occurs to any subject from the time the consent is signed through end of study participation or the initiation of new anti-cancer therapy, whichever is earlier (whether or not related to protocol therapy) must be reported within 24 hours to the Coordinating Center (Attn: [name] – [contact]) using FDA Form 3500A (MedWatch form). The Coordinating Center will then report the event to the FDA using FDA Form 3500A (MedWatch Form).

Additionally, any serious adverse event considered by an investigator (who is a qualified physician) to be related to protocol therapy that is brought to the attention of the study team at any time outside of the time period specified in the previous paragraph also must

be reported immediately to the Coordinating Center using FDA Form 3500A (MedWatch Form).

Any unexpected grade 4 or 5 adverse event and any death during the study period must be reported using FDA Form 3500A (MedWatch form) to the Coordinating Center within one working day (24 hours) of discovery or notification. Please submit the adverse event report using FDA Form 3500A to:

[name]
[name]
[name]
[contact]
[contact]
Email: [contact]

The event should also be reported locally to the site Institutional Review Board (IRB) per local policy.

Otherwise, unexpected serious adverse events must be reported within 15 days.

If the event meets the criteria for FDA mandatory IND safety reporting (serious AND unexpected), the Coordinating Center will report the event to the FDA using FDA Form 3500A (MedWatch form). Events which are assessed as “unexpected fatal or life-threatening” should be reported to FDA by the Coordinating Center as soon as possible, but no later than 7 calendar days following the initial receipt of the information. All other unexpected serious suspected adverse reactions suggesting significant risk to human subjects should be reported to FDA no later than 15 calendar days following the initial receipt of the information.

A copy of all 15 Day Reports and Annual Progress Reports are to be submitted as required by FDA, Pharmaceutical and Medical Devices agency (PMDA) or other local regulators.

All subjects with serious adverse events must be followed up for outcome/resolution for at least 90 days after stopping protocol therapy.

9.5 Routine Adverse Event Reporting

An investigator who is a qualified physician will evaluate all adverse events according to the NCI Common Terminology for Adverse Events (CTCAE), version 4.03. Any adverse event which changes CTCAE grade over the course of a given episode will have each change of grade recorded on the adverse event case report forms/worksheets.

All adverse events regardless of CTCAE grade must also be evaluated for seriousness.

9.6 Data Safety Monitoring Plan

It is the responsibility of the Principal Investigator to oversee the safety of study participants. This safety monitoring will include careful assessment and appropriate reporting of adverse events as noted above.

[figure not shown]
This study will be monitored by the UMGCCC Data and Safety Monitoring and Quality Assurance Committee and will follow the Data Safety and Monitoring Plan as outlined in the Clinical Investigator Handbook of the UMGCCC Clinical Research Office. Monitoring will be conducted as per the plan on file with the University of Maryland IRB (also available in the UMGCCC Clinical Investigator Handbook).

9.7 Secondary AML/MDS

AML/MDS events are now to be reported via AdEERS (in addition to your routine AE reporting mechanisms). In CTCAE v4.0, the event(s) may be reported as either: 1) Leukemia secondary to oncology chemotherapy, 2) Myelodysplastic syndrome, or 3) Treatment-related secondary malignancy. Any malignancy possibly related to cancer treatment (including AML/MDS) should also be reported via the routine reporting mechanisms outlined.

10. PHARMACEUTICAL INFORMATION

10.1 Zydelig (GS-1101, CAL-101) ()

The substance acts as a phosphoinositide 3-kinase inhibitor; more specifically, it blocks P110 δ , the delta isoform of the enzyme phosphoinositide 3-kinase.

10.2 Availability

Zydelig (CAL-101) will be supplied and distributed by Gilead Sciences, Inc. Zydelig is supplied in bottles of 60 tablets of 100 mg and 150 mg strengths. The bottles of Zydelig are white high-density polyethylene with a child-resistant cap and a polyester or cotton coil. The tablet shape is plain-faced, modified oval. The tablets contain the inactive ingredients microcrystalline cellulose, hydroxypropyl cellulose, croscarmellose sodium, sodium starch glycolate, and magnesium stearate. The 100 mg tablets are orange film coated, and the 150 mg tablets are pink film coated. Tablets should be swallowed whole.

10.3 Storage and Stability

Zydelig tablets should be stored at a controlled room temperature of 25°C (77°F), with a range from 15°C (59°F) to 30°C (86°F). While stability of study drug tablets stored at

controlled room temperature has been confirmed, brief excursions to temperatures as low as -10°C or as high as 40°C (eg, during shipping) will not adversely affect the drug. Updated stability data will be provided to the sites, as appropriate. At the end of the study, any remaining unused Zydelig should be destroyed according to local institutional procedures.

Preparation

Zydelig should be dispensed in the original container.

Administration

The prescribed dose of Zydelig should be taken orally. At each dose administration, the tablet number corresponding to the appropriate dose of study drug is to be swallowed whole with 100 to 200 mL (~ 4 to 8 ounces) of water. In case of breakage of the tablets in the oral cavity, additional water should be taken as a rinse.

Zydelig may be taken with or without food. There are no known dietary restrictions related to study drug use.

Overdose Precautions

In Phase 1 studies, an MTD for Zydelig was not reached when administering the drug continuously at dose levels of 350 mg/dose BID (700 mg per day). However, in this protocol, an overdose is defined as administration of more than the prescribed daily study drug (Zydelig) dose (ie, >300 mg in a single day).

In a subject who experiences an overdose, consideration should be given as to whether study drug administration should be temporarily interrupted. If the overdose ingestion is recent and substantial, and if there are no medical contraindications, use of gastric lavage or induction of emesis may be considered. Observation for any symptomatic side effects should be instituted, and biochemical and hematological parameters should be followed closely (consistent with the protocol or more frequently, as needed). Appropriate supportive management to mitigate adverse effects should be initiated.

Inadvertent Exposure and Spill Precautions

Based on available data from nonclinical studies, Zydelig does not appear to be acutely toxic, genotoxic, or irritative at levels that are likely to result from inadvertent exposure to the contents of broken tablets. However, personnel handling the drug should use reasonable precautions to avoid eye contact, skin contact, inhalation, or ingestion of the study drug product. For further information regarding inadvertent exposure and spill precautions, please consult the Zydelig investigator brochure.

10.4 Pharmacokinetics

Absorption

Following oral administration of a single dose of Zydelig in the fasted state, the median T_{max} was observed at 1.5 hours. Idelalisib exposure increased in a less than dose-proportional manner over a dose range of 50 mg to 350 mg twice daily in the fasted state. Relative to fasting conditions, the administration of a single dose of Zydelig with a highfat meal increased idelalisib AUC 1.4-fold. Zydelig can be administered without regard to food.

Distribution

Idelalisib is greater than 84% bound to human plasma proteins with no concentration dependence. The mean blood-to-plasma ratio was 0.7. The population apparent central volume of distribution at steady state is 23 L

Metabolism and Elimination

Idelalisib is metabolized to its major metabolite GS-563117 via aldehyde oxidase and CYP3A. GS-563117 is inactive against PI3K δ in vitro. Idelalisib undergoes minor metabolism by UGT1A4. The population apparent systemic clearance at steady-state is 14.9 L/hr. The population terminal elimination half-life of idelalisib is 8.2 hours. Following a single dose of 150 mg of [¹⁴C] idelalisib, 78% and 14% of the radioactivity was excreted in feces and urine, respectively. GS-563117 accounted for 49% of the radioactivity in the urine and 44% in the feces.

Specific Population

Age, Gender, Race and Weight

Population pharmacokinetic analyses indicated that age, gender, race, and weight had no effect on idelalisib exposure.

Patients with Renal Impairment

A pharmacokinetic study following a single dose of 150 mg of Zydelig was performed in healthy subjects and subjects with severe renal impairment (CrCl 15 to 29 mL/min). Creatinine clearance had no effect on idelalisib exposure. No dose adjustment is needed for patients with CrCl \geq 15 mL/min.

Patients with Hepatic Impairment

A pharmacokinetic study of Zydelig was performed in healthy subjects and subjects with hepatic impairment. The geometric mean AUC increased up to 1.7-fold in subjects with ALT or AST or bilirubin values greater than the upper limit of normal (ULN) compared to subjects with normal AST or ALT or bilirubin values. Limited safety and efficacy data are available for patients with baseline AST or ALT greater than 2.5 x ULN or bilirubin greater than 1.5 x ULN, as these patients were excluded from Studies 1 and 2. Patients with baseline hepatic impairment should be monitored for signs of Zydelig toxicity.

Drug Interactions

In Vitro Studies

Idelalisib is a substrate for aldehyde oxidase, CYP3A, and UGT1A4 in vitro. Idelalisib inhibits CYP2C8, CYP2C19, CYP3A, and UGT1A1 and GS-563117 inhibits CYP2C8, CYP2C9, CYP2C19, CYP3A and UGT1A1 in vitro. Idelalisib and GS-563117 are not likely to inhibit CYP1A, CYP2B6, and CYP2D6. Idelalisib induces CYP2B6 and CYP3A4, but does not induce CYP1A2 in vitro. GS-563117 does not induce these enzymes. Idelalisib and GS-563117 are substrates of P-glycoprotein (P-gp) and BCRP in vitro. Idelalisib is not a substrate of OATP1B1, OATP1B3, OAT1, OAT3, or OCT2. GS-563117 is not a substrate of OATP1B1 or OATP1B3. Idelalisib inhibits P-gp, OATP1B1, and OATP1B3, and GS-563117 inhibits OATP1B1, OATP1B3 in vitro. Idelalisib is not likely to inhibit BCRP, OCT2, OAT1, or OAT3, and GS-563117 is not likely to inhibit P-gp, BCRP, OCT2, OAT1, or OAT3.

Effect of Other Drugs on Idelalisib

A single dose of 150 mg of Zydelig was administered alone and after rifampin (a strong CYP3A and P-gp inducer) 600 mg once daily for 8 days in healthy subjects. Rifampin decreased the geometric mean idelalisib AUC by 75% and the geometric mean C_{max} by 58%. Avoid coadministration of Zydelig with strong CYP3A and P-gp inducers. A single dose of 400 mg of Zydelig was administered alone and after ketoconazole (a strong CYP3A and P-gp inhibitor) 400 mg daily for 4 days in healthy subjects. Ketoconazole increased the geometric mean idelalisib AUC by 1.8-fold. No changes in the geometric mean C_{max} were observed. Patients taking concomitant CYP3A inhibitors should be monitored for signs of Zydelig toxicity

Effect of Idelalisib on Other Drugs

A single oral dose of midazolam 5 mg was administered alone and after Zydelig 150 mg for 15 doses in healthy subjects. The geometric mean midazolam C_{max} increased by 2.4-fold and the geometric mean midazolam AUC increased by 5.4-fold. Avoid coadministration of Zydelig with CYP3A substrates, as Zydelig is a strong CYP3A inhibitor. A single dose of 10 mg of rosuvastatin (OATP1B1 and OATP1B3 substrate) was administered alone and after Zydelig 150 mg for 12 doses in healthy subjects. No changes in exposure to rosuvastatin were observed. A single dose of 0.5 mg of digoxin (P-gp substrate) was administered alone and after Zydelig 150 mg for 19 doses in healthy subjects. No changes in exposure to digoxin were observed.

10.5 Toxicity.

Hepatotoxicity

Fatal and/or serious hepatotoxicity occurred in 18% of patients treated with Zydelig monotherapy and 11% of patients treated with Zydelig in combination trials. Elevations in ALT or AST greater than 5 times the upper limit of normal have occurred. These findings were generally observed within the first 12 weeks of treatment and were reversible with dose interruption. After resumption of treatment at a lower dose, 26% of patients had recurrence of ALT and AST elevations. Discontinue Zydelig for recurrent hepatotoxicity. Avoid concurrent use of Zydelig with other drugs that may cause liver toxicity. Monitor ALT and AST in all patients every 2 weeks for the first 3 months of treatment, every 4 weeks for the next 3 months, then every 1 to 3 months thereafter. Monitor weekly for liver toxicity if the ALT or AST rises above 3 times the upper limit of normal until resolved. Withhold Zydelig if the ALT or AST is greater than 5 times the upper limit of normal, and continue to monitor AST, ALT and total bilirubin weekly until the abnormality is resolved.

Severe Diarrhea or Colitis

Severe diarrhea or colitis (Grade 3 or higher) occurred in 14% of patients treated with Zydelig monotherapy and 19% of patients treated with Zydelig in combination trials. Diarrhea can occur at any time. Avoid concurrent use of Zydelig and other drugs that cause diarrhea. Diarrhea due to Zydelig responds poorly to antimotility agents. Median time to resolution ranged between 1 week and 1 month across trials, following interruption of Zydelig therapy and in some instances, use of corticosteroids.

Pneumonitis

Fatal and serious pneumonitis occurred in patients treated with Zydelig. In randomized clinical trials of combination therapies, pneumonitis occurred in 4% of patients treated

with Zydelig compared to 1% on the comparator arms. Time to onset of pneumonitis ranged from <1 to 15 months. Patients taking Zydelig who present with pulmonary symptoms such as cough, dyspnea, hypoxia, interstitial infiltrates on a radiologic exam, or a decline by more than 5% in oxygen saturation should be evaluated for pneumonitis. If pneumonitis is suspected, interrupt Zydelig until the etiology of the pulmonary symptoms has been determined. Patients with pneumonitis thought to be caused by Zydelig have been treated with discontinuation of Zydelig and administration of corticosteroids.

Infections

Fatal and/or serious infections occurred in 21% of patients treated with Zydelig monotherapy and 36% of patients treated with Zydelig in combination trials. The most common infections were pneumonia, sepsis, and febrile neutropenia. Monitor patients for signs and symptoms of infection and interrupt Zydelig for Grade 3 or higher infection. Serious or fatal *Pneumocystis jirovecii* pneumonia (PJP) or cytomegalovirus (CMV) occurred in <1% of patients treated with Zydelig. Consider prophylaxis for PJP. Interrupt Zydelig in patients with suspected PJP infection of any grade, and permanently discontinue Zydelig if PJP infection of any grade is confirmed. Interrupt Zydelig in the setting of positive CMV PCR or antigen test until the infection has resolved. If Zydelig is subsequently resumed, patients should be monitored (by PCR) for CMV reactivation at least monthly.

Intestinal Perforation

Fatal and serious intestinal perforation occurred in Zydelig-treated patients. At the time of perforation, some patients had moderate to severe diarrhea. Advise patients to promptly report any new or worsening abdominal pain, chills, fever, nausea, or vomiting. Discontinue Zydelig permanently in patients who experience intestinal perforation

Severe Cutaneous Reactions

Fatal cases of Stevens-Johnson syndrome (SJS) and toxic epidermal necrolysis (TEN) have occurred in patients treated with Zydelig. If SJS or TEN is suspected, interrupt Zydelig until the etiology of the reaction has been determined. If SJS or TEN is confirmed, permanently discontinue Zydelig. Other severe or life-threatening (Grade ≥ 3) cutaneous reactions, including dermatitis exfoliative, rash, rash erythematous, rash generalized, rash macular, rash maculo-papular, rash papular, rash pruritic, exfoliative rash, and skin disorder, have been reported in Zydelig-treated patients. Monitor patients for the development of severe cutaneous reactions and discontinue Zydelig.

Anaphylaxis

Serious allergic reactions, including anaphylaxis, have been reported in patients on Zydelig. In patients who develop serious allergic reactions, discontinue Zydelig permanently and institute appropriate supportive measures.

Neutropenia

Treatment-emergent Grade 3 or 4 neutropenia occurred in 25% of patients treated with Zydelig monotherapy and 46% of patients treated with Zydelig in combination trials. Monitor blood counts closely.

Embryo-fetal Toxicity

Based on findings in animals, Zydelig may cause fetal harm when administered to a pregnant woman. Idelalisib is teratogenic in rats, at systemic exposures 12 times those reported in patients at the recommended dose of 150 mg twice daily. Advise females of reproductive potential to avoid becoming pregnant while taking Zydelig. If contraceptive methods are being considered, use effective contraception during treatment, and for at least 1 month after the last dose of Zydelig.

11. CORRELATIVE STUDIES

Please see Appendix D

12. DATA REPORTING/REGULATORY CONSIDERATIONS

Clinical data will be entered into the OnCore[®] database by performing site personnel. Information can be entered into OnCore[®] in a way that is 21CFR11.10 (electronic medical records) compliant. OnCore[®] is equipped for HIPAA-compliant internet-based entry of protocol tracking and review information.

All study data will be collected by the research team at each and every study visit and recorded in the research record. This data will then be entered in to the OnCore[®] study database.

All source documents will be obtained and retained along with any study forms, and placed into the patient's research record.

ADMINISTRATIVE AND REGULATORY DETAILS

This study will be conducted in accordance with current U.S. Food and Drug Administration (FDA) Regulations, Good Clinical Practices (GCPs) and International Counsel on Harmonization (ICH) E6 Guidelines.

Under the terms of the Food and Drug Administration Modernization Act (FDAMA) and the Food and Drug Administration Amendments Act (FDAAA), the trial and its results will be submitted to the Clinical Trials Data Bank, <http://www.clinicaltrials.gov>.

Information posted will allow subjects to identify potentially appropriate trials for their disease conditions and pursue participation by calling a central contact number for further information on appropriate trial locations and trial site contact information.

Institutional Review Board (IRB)

This protocol will be submitted to the University of Maryland IRB. Study procedures will begin once IRB approval is secured. All amendments, instances of reportable new information (i.e. unanticipated problems, data breaches, etc.) and continuing review reports will be submitted to the University of Maryland IRB.

13. Clinical Trial Monitoring

Data safety and verification monitoring will be conducted in accordance with the Greenebaum Cancer Center Sponsor-Investigator Monitoring Standard Operating Procedure (SOP), the Code of Federal Regulations (CFR), and FDA and International Counsel on Harmonization (ICH) E6 Guidelines.

14. STATISTICAL CONSIDERATIONS

A true proportion of study subjects that are not removed from the study for toxicity or intolerance of 0.70 or higher will be considered satisfactory in this particular patient population. If the true proportion of severe toxicity -free patients is 50% or less, then Zydelig will not be considered a promising maintenance treatment post Autologous stem cell transplantation due to unacceptable toxicity.

A single-stage open-label design will be used for the study. With 34 eligible patients on the study, the Type I error or probability of declaring drug desirable if the proportion of subjects removed from study due to toxicity or intolerability is 0.50 or higher, is 0.075. The probability of rejecting the Zydelig as unacceptable due to severe toxicity compound if the proportion of subject who developed severe toxicity is less or equal to 30% rate is less than 20%. Hence, the study will have an adequate about 80% power. Addressing the safety of Zydelig, a maximum width 90% confidence interval for any grade 3 or higher toxicity will be about 32%, assuming that a total of 31 patients are enrolled. For instance, if 3 out of 31 patients (10%) develop grade 3 or higher non-hematologic toxicity, then a 90% confidence interval for the true toxicity rate is between 3% and 24%. For 31 patients in this study, if the true unknown probability of a rare toxicity is 10%, the probability of observing 1 or more toxicities is 96%, for 5% it is 80%, and if the true toxicity rate is 3% then the probability of observing one or more rare toxicities is 61%.

We plan to accrue 34 eligible patients to account for about 10% possible drop-out

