Toxicities will be evaluated to include standard hematologic toxicities for solid tumors (i.e. count suppression etc.). Dose reductions will be pursued as described below for both hematologic and non-hematologic toxicities grade 2 and above

Initial dose will be 150 mg PO BID. Dose modifications for toxicities due to Zydelig will follow the package insert recommendations as below. For other severe or life-threatening toxicities related to Zydelig, withhold drug until toxicity is resolved. If resuming Zydelig after interruption for other severe or life-threatening toxicities, reduce the dose to 100 mg twice daily. Recurrence of other severe or life-threatening Zydelig-related toxicity upon rechallenge should result in permanent discontinuation of Zydelig. Toxicity, as well as graft failure will be monitored continuously throughout the trial.

Statistical Methods:

We are studying a cohort of 34 patients with iNHL or tiNHL. A single-stage open-label design will be used for the study. Please see section 14.0 Statistical Considerations for more information.

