7. DOSING DELAYS/DOSE MODIFICATIONS

Please refer to table 2 below.

Patients who experience a Grade 2 or 3 toxicity and recover to \leq Grade 1 (or to pretreatment baseline level of toxicity) may continue treatment at the next lower dose level (i.e., Dose level 2 down to dose level 1).

Once the dose has been reduced, patients must remain at the reduced dose for 28 days. Dose escalation may occur at the discretion of the investigator and may occur every 28 days. Patients may have their dose de-escalated from level 2 to level 1, three times before being removed from treatment.

Please note:

- There are no dose escalations above 150 mg BID
- There are no dose reductions below 100 mg BID

Table 2

Dose Modification Schedule	
Dose Level	Dose of Zydelig
Level 2 (starting dose)	150 mg PO BID
Level 1	100 mg PO BID

Table 3

Dose Modifications for Toxicities Due to Zydelig

Pneumonitis	Any symptomatic pneumonitis		
	Discontinue Zydelig in patients with any severity of symptomatic pneumonitis		
ALT/AST	>3.0-5.0 x ULN	>5-20 x ULN	>20 x ULN
	Decrease Zydelig to 100 mg BID and monitor weekly until ≤ 1 x ULN.	Withhold Zydelig. Monitor at least weekly until ALT/AST are ≤ 1 x ULN, then may resume Zydelig at 100 mg BID.	Discontinue Zydelig permanently.
Bilirubin	>1.5-3 x ULN	>3-10 x ULN	>10 x ULN

	Decrease Zydelig to 100 mg BID. Monitor at least weekly until ≤ 1 x ULN.	Withhold Zydelig. Monitor at least weekly until bilirubin is ≤ 1 x ULN, then may resume Zydelig at 100 mg BID.	Discontinue Zydelig permanently.
Diarrhea*	Moderate diarrhea	Severe diarrhea or hospitalization	Life-threatening diarrhea
	Decrease Zydelig to 100 mg BID. Monitor at least weekly until resolved.	Withhold Zydelig. Monitor at least weekly until resolved, then may resume Zydelig at 100 mg BID.	Discontinue Zydelig permanently.
Neutropenia[^]	ANC 1.0 to <1.5 Gi/L	ANC 0.5 to <1.0 Gi/L	ANC <0.5 Gi/L
	Maintain Zydelig dose.	Decrease Zydelig to 100 mg BID. Monitor ANC at least weekly.	Interrupt Zydelig. Monitor ANC at least weekly until ANC ≥ 0.5 Gi/L, then may resume Zydelig at 100 mg BID.
Thrombocytopenia	Platelets 50 to <75 Gi/L	Platelets 25 to <50 Gi/L	Platelets <25 Gi/L
	Maintain Zydelig dose.	Decrease Zydelig to 100 mg BID Monitor platelet counts at least weekly.	Interrupt Zydelig. Monitor platelet count at least weekly. May resume Zydelig at 100 mg BID when platelets ≥ 25 Gi/L.

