14.1 Study Design/Primary Endpoints

This single cohort open-label study will accrue 34 patients with iNHL or tiNHL. The biologically active dose of Zydelig will be 1st used at 100/150 mg PO BID. Within patient dose reductions are allowed for hematologic and non-hematologic toxicities above grade 2. The proportion of patients removed from the study due to toxicity will be reported, along with all toxicities specified by type and grade.

Early stopping guideline for toxicity: Toxicity will be monitored continuously. If it becomes evident that the proportion of patients being removed from the study for toxicity convincingly exceeds 50%, the study will be halted for a safety consultation. The toxicity stopping rule will hold enrollment.

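### Section 14 states one 0.50-versus-0.70 toxicity decision on two different events, prints no cutoff, and gives for 34 patients a type I error that belongs to 31

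*Combined protocol and SAP*

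**What the plan says.** Section 14 describes a single-stage design through four decision sentences.

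- Satisfactory limit, on removal: a true proportion of "study subjects that are not removed from the study for toxicity or intolerance of 0.70 or higher".
- Not-promising limit, on severe toxicity: "If the true proportion of severe toxicity -free patients is 50% or less, then Zydelig will not be considered a promising maintenance treatment".
- Type I error, on removal: with 34 eligible patients, the probability of declaring the drug desirable if "the proportion of subjects removed from study due to toxicity or intolerability is 0.50 or higher, is 0.075".
- Type II error, on severe toxicity: the probability of rejecting the drug "if the proportion of subject who developed severe toxicity is less or equal to 30% rate is less than 20" per cent, summarised as about 80% power.

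The precision statements that follow use a third term, grade 3 or higher, and assume 31 patients. The section closes with "We plan to accrue 34 eligible patients to account for about 10% possible drop-out". Section 14.1, headed Study Design/Primary Endpoints, says: "The proportion of patients removed from the study due to toxicity will be reported", together with all toxicities by type and grade. Its early stopping guideline also uses removal for toxicity and 50%, without a number of patients. No number of patients is printed as the end-of-trial cutoff in Section 14, 14.1 or 14.2.

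**The concern.** A one-sample test needs one event, with both limits and both error rates defined on it. Here the null and alternative limits sit on different events, and so do the two error rates. Toxicity and safety is the sole primary objective, and these sentences are its only end-of-trial decision. A drug can cause many severe but reversible toxicities and few removals, so the event that is counted could affect the conclusion. With neither the event fixed in every sentence nor a cutoff printed, an analyst has to infer the rule. The type I error is part of the same problem: if 0.075 does not follow from 34 patients, the stated sample size cannot be used to recover the cutoff.

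**Working it through.** **1. Are the events the same under the protocol's rules?**

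- Severe toxicity without removal. For severe diarrhea, Table 3 in Section 7 says: "Withhold Zydelig. Monitor at least weekly until resolved, then may resume Zydelig at 100 mg BID". ALT/AST above 5 and up to 20 times ULN is handled in the same way. Section 7.1 lets other related grade 3 non-hematologic toxicity resume one dose level lower. The Synopsis says: "If resuming Zydelig after interruption for other severe or life-threatening toxicities, reduce the dose to 100 mg twice daily".
- Treatment ended whatever the severity. Table 3 and Section 10.5 end treatment for confirmed Pneumocystis pneumonia of any severity or grade.

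So neither event contains the other.

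**2. Reproducing the printed error rates.** Inputs from Section 14: removal 0.50 under the null, 0.30 (1 − 0.70) under the alternative, n = 34 as stated, or 31 as used for precision. With X the number removed and the drug declared acceptable if X ≤ c:

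- alpha = P(X ≤ c | n, 0.50)
- power = P(X ≤ c | n, 0.30)

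For n = 31 and c = 11, alpha = 160,645,504 / 2^31 = 0.0748. For n = 34 and c = 12, alpha = 1,043,243,132 / 2^34 = 0.0607. The cutoffs are inferred, since none is printed.

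| n | c | alpha | power |
|---|---|---|---|
| 30 | 10 | 0.0494 | 0.7304 |
| 30 | 11 | 0.1002 | 0.8407 |
| 31 | 10 | 0.0354 | 0.6879 |
| 31 | 11 | 0.0748 | 0.8076 |
| 31 | 12 | 0.1405 | 0.8931 |
| 32 | 11 | 0.0551 | 0.7717 |
| 32 | 12 | 0.1077 | 0.8674 |
| 33 | 11 | 0.0401 | 0.7334 |
| 33 | 12 | 0.0814 | 0.8387 |
| 34 | 11 | 0.0288 | 0.6932 |
| 34 | 12 | 0.0607 | 0.8071 |
| 34 | 13 | 0.1147 | 0.8897 |

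No cutoff at 34 gives 0.075. At 31, c = 11 gives 0.0748, which rounds to the printed value, with type II error 1 − 0.8076 = 0.192, below 20%. Only 31 (c = 11) and 34 (c = 12) keep alpha at or below 0.075 and power at or above 0.80; 30, 32 and 33 have no such cutoff.

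**3. Cross-check that 31 was the working number.** Section 14 prints 96%, 80% and 61% for seeing at least one toxicity with true rate 10%, 5% and 3%. The formula 1 − (1 − p)^31 gives 0.962, 0.796 and 0.611; with 34 it gives 0.972, 0.825 and 0.645. Also, 34 × 0.9 = 30.6, which fits the 10% drop-out allowance.

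**4. How much could the event matter?** With the inferred rule X ≤ 12 of 34, the chance of declaring the drug acceptable at an assumed true rate is:

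| true event rate | 0.20 | 0.30 | 0.40 | 0.50 | 0.60 |
|---|---|---|---|---|---|
| P(acceptable) | 0.989 | 0.807 | 0.354 | 0.061 | 0.003 |

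The documents give no expected removal rate. For severe events, the tables in Section 9.2 report grade 3 or higher diarrhea in 20, pneumonia in 23, ALT in 20 + 7 = 27 and neutrophils in 20 + 16 = 36 of 146 monotherapy patients, with no information on overlap. The share with at least one of these four could lie anywhere from 36/146 = 25% (full overlap) to 106/146 = 73% (none). That population was not on post-transplant maintenance, so this shows only that the rate is not pinned down.

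**The case against.** The strongest reply is that this is loose wording for one endpoint. Section 14.1 carries the primary-endpoint heading, the only summary proportion it names is removal, and its halt guideline uses the same event and the same 50%. The 0.70/30% and 50% figures in Section 14 form a single binomial test. This largely stands: removal is very probably what was meant. A reader might infer that the trial has no primary endpoint, or that the event is free to be picked after the data are seen. The documents do not support that much. What remains is that two of the four decision sentences name another event.

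Nor is the word severe without meaning elsewhere. Table 7 attaches it to CTCAE grade 3, and Section 10.5 uses it for grade 3 or higher diarrhea and skin reactions. That stands too, but Section 14 does not refer to those places and uses grade 3 or higher as a separate term.

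A reader might also infer an inflated false-positive risk. At 34 with at most 12 removed, the true figure is lower than printed (0.061 against 0.075) and power is still 0.81, so the slip is conservative. It would be anti-conservative only with at most 13.

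Finally, a contrast such as 0.99 against 0.06 (20% removed, 50% with a severe toxicity) uses assumed rates. If both rates are 30%, the chance is 0.81 on either event. Some reversible events also become removals: Section 10.5 reports 26% recurrence of ALT/AST elevation after resumption at a lower dose and calls for discontinuation if hepatotoxicity recurs.

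**Conclusion.** The point holds in a limited form. Section 14 states one decision on two events that the protocol's own rules keep distinct, does not define one of them, and prints no cutoff. Its type I error of 0.075 does not belong to the 34 patients it is stated for; it belongs to at most 11 of 31. The numerical slip is small and in the safe direction under the only cutoff at 34 that keeps both printed rates. The practical effect of the two-event wording cannot be sized from the documents, because it depends on the gap between the removal rate and the severe-toxicity rate, and that gap is not given. The calculations assume an exact one-sided binomial test of 0.50 against 0.30 removed, with inferred cutoffs. This should be fixed, but it is a correction of wording and specification and does not invalidate the design.

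**What to change.** 1. Use removal for toxicity or intolerance in all four decision sentences of Section 14, matching 14.1, and define it as stopping study treatment for that reason. Section 5.5 names only progression as a ground for removal from study; align it with Sections 5.3 and 5.4, which already provide for ending treatment or removal for unacceptable adverse events.
2. State the time window and the denominator, and say how patients who stop early for progression, withdrawal or other reasons are counted.
3. Print the cutoff with its true error rates: acceptable if at most 12 of 34 are removed (alpha 0.061, power 0.81), or at most 11 of 31 (0.075, 0.81). Correct the sentence that gives 0.075 for 34. For other evaluable numbers, state in advance which error rate gives way.
4. Keep severe toxicity out of the decision sentences and report grade 3 or higher toxicity separately with its 90% confidence interval, as already planned.

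The cost is a short amendment, preferably before outcome data are reviewed. The sample size is unchanged. The adverse event form (Table 7) already asks whether an event led to discontinuation; stopping for intolerance or at patient or physician discretion, which Section 5.1 allows, may need a separate reason field. The protocol also conflicts on when treatment is stopped or held for CMV, pneumonitis, and grade 4 or life-threatening toxicity. That is a separate matter for the sponsor to reconcile, and no clinical rule is proposed here.
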